3.3 Inflammation as part of lung pathology in COVID-19

Following initial infection of the nasal pharyngeal epithelium, SARS-CoV-2 infection can spread to the lungs where it causes viral pneumonia, producing symptoms of dyspnea secondary to hypoxemia (2, 14), with radiographs showing interstitial infiltrates in the lung periphery (3, 4), collectively creating a novel disease entity termed COVID-19. Severe pneumonia can progress to Adult Respiratory Distress Syndrome (ARDS) requiring intubation and mechanical ventilation (1, 2). The development of severe pneumonia and respiratory failure leading to ARDS has been associated with elevated levels of serum cytokines (1, 6), suggesting that SARS-CoV-2 pulmonary infection in these patients has led to a “cytokine storm”, and that administration of drugs that inhibit cytokine release or block cytokine signaling may be of clinical benefit in patients with COVID-19. A recent report from Wuhan described 548 hospitalized patients with COVID-19, half of whom had severe disease (defined by the 2019 American Thoracic Society Guidelines (16)) of which one third required mechanical ventilation and one third died (1). Age, male gender, elevated leukocyte counts, LDH, troponin and glucose levels were associated with an increased risk of death among COVID-19 patients with severe disease in a multi-variable model, and treatment with steroids, a non-specific immunosuppressive, were associated with an increased risk of death. Serum cytokine levels for IL-2R, IL-6, IL-10, and TNF- α were significantly higher in COVID-19 patients with severe disease than nonsevere patients (1). These data and other reports of similar findings indicate that 1) patients with severe disease at a higher risk of death can be identified by simple clinical and laboratory assessments, 2) that disease severity is associated with a heightened inflammatory state, and 3) interventional studies to reduce inflammation in patients with high-risk disease could be of benefit to patients. A separate analysis of Wuhan patients with severe COVID-19 indicated that patients with severe disease had decreased numbers of total T cells, CD8+T cells and CD4+T cells, and that lower T cell numbers were negatively correlated with patient survival (17). Of note, lower T cell numbers in patients were also associated with higher IL-6, IL-10 and TNF- α cytokine levels, and COVID-19 patients treated in the ICU had higher levels of expression of the co-inhibitory markers PD-1, LAG-3 and TIM-3 (17), suggesting that inflammation may cause quantitative and qualitative suppression of T cell function.

3.4 Phosphoinositide 3-Kinase (PI3K)

PI3K proteins are divided into three classes of which only Class IA PI3K molecules have been implicated in human cancers, prompting development of isoform-selective inhibitors to Class IA PI3K (18). Analysis of evolutionary conservation across known class I PI3K signaling cascades reveals the greatest conservation in signaling along the insulin/IGF-1/AKT pathway, suggesting PI3K primarily evolved to regulate cellular proliferation and metabolic changes in response to glucose (18).

PI3Ks are involved in the generation of lipid second messengers and contain eight catalytic subunits of PI3K, with the P110 gamma and the P110 delta subunits being expressed at much higher levels in immune cells (19, 20). The PI3K p110 subunits work by phosphorylating phosphatidylinositol 4,5 bisphosphate (PIP2) into phosphatidylinositol 3, 4,5 triphosphate (PIP3), which enables anchorage and association of cytosolic proteins near the lipid bilayer, enabling complex signal transduction cascades to occur (18). In the case of T cells, metabolism of glucose is closely linked to the replicative capacity of the cells, with T cells capable of oxidative phosphorylation exhibiting enhanced replicative capacity whereas T cells that rely upon glycolysis exhibit reduced replicative potential, as reviewed (21).

PIP3 then goes on to function as a second messenger that initiates multiple signaling cascades, including the phosphorylation of AKT, a serine/threonine protein kinase, leading to downstream survival and differentiation signals for example through mechanistic target of rapamycin 1 (mTOR) also a serine/threonine kinase(22). Upon T cell activation, there is an increase in uptake of amino acids and glucose leading to activation of mTOR1 and this activation is required to maintain the T cell effector functions (23–26). Activation of mTOR1 also promotes induction of aerobic glycolysis, as well as assistance in maintaining it, which leads to increased differentiation and effector functions, which are shown to be less efficacious in terms of adoptive T cell therapies (26). By inhibiting mTOR through inhibition of PI3K. PI3K inhibitors promote formation of a pool of T-cells with a memory phenotype by inhibiting aerobic glycolysis and preventing terminal differentiation (26). Given that Daio et al. showed that CD8 and CD4 T-cells in COVID-19 patients increase expression of PD-1 and TIM-3 as their clinical symptoms worsen(17), we propose that duvelisib may mitigate T-cell exhaustion to promote more effective anti-viral responses to COVID-19, thus preventing COVID-19 infection progression.

3.5 Pre-Clinical Pharmacology of duvelisib and T cell activation and expansion

Duvelisib is a highly potent, PI3K delta and gamma inhibitor with a whole blood IC₅₀ of 0.36nM for inhibition of the delta subunit and whole blood IC₅₀ of 19.6nM for inhibition of the gamma subunit (11). We have seen that human T cells from healthy volunteers and chronic lymphocytic leukemia (CLL) patients show a doubling in net expansion at concentrations of duvelisib from 40nM to 0.4 μ M over a 9-14 day culture period ((9) and unpublished data). Of note, high dimensional profiling of T cells showed less effector T cells and a shift in the metabolic profile of T cells from dependency on glucose to glutamine and lower levels of expression of co-inhibitory markers PD-1, TIM-3 and LAG-3 (unpublished). Furthermore, models of the human CLL cell line OSU-CLL engrafted to NOG mice show that duvelisib-cultured chimeric antigen receptor (CAR) T-cells exhibit enhanced in vivo proliferation, greater CD8:CD4 CAR ratios, and enhanced efficacy (unpublished data). Taken together, this data indicates that a short-term exposure of T cells to duvelisib is not globally immunosuppressive but instead preserves qualitative measures of T cell function while reducing effector T cell differentiation and preserving naïve and memory subsets.

3.6 PI3K inhibitors in clinical settings

PI3-kinase (PI3K) inhibitors are FDA-approved for treatment of relapsed follicular lymphoma (FL) and CLL/small lymphocytic lymphoma (SLL). Orally bioavailable drugs are typically dosed once or twice a day with the goal of inhibiting signaling through the PI3K-AKT pathway causing reduction in the growth of malignant lymphoma cells and induction of apoptosis. PI3K inhibitors are generally well tolerated and can be given for weeks to months as continuous therapy without significant hematological toxicity. One common feature of treatment with PI3K inhibitors is the development of late autoimmune disease, typically after more than 1 month of drug exposure, including colitis, pneumonitis and rash, that appears to be a consequence of blocking differentiation and down-regulation of regulatory T cells (12, 27).

4. Study Intervention/Investigational Agent

4.1 Description (duvelisib)

Duvelisib is an oral PI3K inhibitor. FDA approved duvelisib (Copiktra, IPI-145) on September 24, 2018. Duvelisib is approved for the treatment of adult patients with relapsed or refractory CLL/SLL after at least two prior therapies, and relapsed or refractory follicular lymphoma (FL) after at least two prior systemic therapies. Refer to the approved labeling for more details on specific indications and for detailed information on duvelisib.

4.2 Drug handling

4.2.1 Acquisition and Accountability

Duvelisib and unmatched placebo capsule (same size and shape but slightly different shade of blue/green) will be provided by Verastem and will be packaged and labeled by Verastem. The study drug provided for this study will be used only as directed in the study protocol. The IDS (Investigational Drug Service) personnel at each site will account for all study drugs. Drug accountability should be performed until the patient stops study treatment completely. Study site personnel will account for all study drugs received at the site. Study drug supplies must be kept in an appropriate, secure locked area and stored in accordance with the conditions specified on the labels. The Investigator, pharmacist, or designee must maintain an accurate record of dispensing the study drug/s in a Drug Accountability Log.

The Drug Accountability Log may record specifics to study drug dispensation such as:

- Records of product delivery, inventory, temperature monitoring, destruction, and return.
- Dosages prepared, time prepared, doses dispensed.
- Doses destroyed.
- The Drug Accountability Log will be reviewed by the monitor during site visits and at the completion of the study.

The study drug supply will be disposed of as per Winship's Investigational Pharmacy (IDS) SOP. Duvelisib/study drug capsule should be taken at approximately the same times on each day. Duvelisib/study drug capsule should be taken with 8 oz of water if possible. Compliance will be assessed by the investigator and/or study personnel and information provided by the Hospital electronic medical record will be captured in the Drug Accountability Form. Dose changes and interruptions of study drug must be specifically documented in the patient source documents and eCRF. The time of each dose should be reported in the Hospital electronic medical record. Patients will not be allowed to make up missed doses and a missed dose should also be recorded in the Hospital electronic medical record. Damaged medication will be replaced.

4.2.2. Formulation, Appearance, Packaging and Labeling

Duvelisib comes in two strengths: 15mg and 25mg capsules. A placebo capsule matched in size and shape with similar color to the 25 mg duvelisib capsule will be provided by Verastem. Twenty-eight (28) 25mg duvelisib tablets or placebo capsule will be dispensed to the in-patient unit for each enrolled patient. 15mg duvelisib tablets are also available if needed for dose reduction. All duvelisib and placebo capsules will be over-encapsulated at the Emory Investigational Pharmacy so that they appear identical, to avoid unblinding due to differences in duvelisib and placebo capsule color.

4.2.3. Product Storage and Stability

Duvelisib/placebo will be stored at the Emory Investigational Pharmacy. Duvelisib/study drugs will be stored at room temperature between 20-25 degrees Celsius.

4.2.4. Study Drug Administration:

Duvelisib/placebo is an oral medication that will be taken twice a day. The intent of the study design is to conduct a placebo-controlled double-blinded/double-masked administration of duvelisib or placebo in hospitalized

Protocol Title: Duvelisib Ameliorates Manifestations of Pneumonia in Established Novel Coronavirus Infection (DAMPEN-CI)

patients with severe COVID-19. All efforts will be undertaken to maintain ignorance among clinical and study staff as to allocation of each individual patient to active drug versus placebo—Subjects, the clinical team (physicians, nurses, advanced practice providers (nurse practitioner/physician assistant), clinical pharmacists) will not be informed as to whether an individual subject is receiving active drug or placebo.

4.2.5 Interruption/Disruption of Treatment:

Duvelisib/placebo is a BID medication. Medication doses that are missed or not absorbed (i.e., vomiting) will not be made up with additional dosing.

Duvelisib can be stopped if any of the following are observed:

- Grade 3 or 4 hematologic toxicity (19) as defined by the NCI CTCAE v5.0.
- Grade 3 or 4 non-hematological toxicity

Study drug (duvelisib or placebo) will be stopped at the time of hospital discharge if that occurs prior to day 15.

Grades 1-2 AEs as defined by the NCI CTCAE, version 5.0 will not result in any dose modifications and will be treated with supportive care. If study drug is stopped due to an AE, it will not be resumed.

5. Study Procedures

5.1 Study Design

This is a prospective placebo-controlled, double-blinded/double-masked phase 2 clinical trial study of treating patients with severe COVID-19 disease who do not require mechanical ventilation at randomization with the FDA-approved dose of duvelisib for a maximum of 14 days.

Rationale for study design

Duvelisib is proposed as an immunomodulatory drug that can reduce the generation of inflammatory cytokines in patients with severe COVID-19 while preserving quantitative and qualitative T cell function. A two-week exposure to duvelisib has been chosen because clinical deterioration of patients with severe COVID-19 typically occurs within this time frame, and we have demonstrated enhanced T cell expansion and decreased expression of markers associated with T cell exhaustion and senescence in T cells co-cultured with duvelisib for 14 days in both healthy controls, CLL and DLBCL patients. While longer exposure to duvelisib might be considered, it is appropriate for an initial study to limit the duration of exposure to reduce the risk of secondary opportunistic infections associated with long-term exposure and to potentially preserve B cell function and humoral responses to SARS-CoV-2.

Justification for Duvelisib Dose

In the phase I study with duvelisib in hematological malignancies, the maximum tolerated dose (MTD) was 75 mg BID. However, peak inhibition of the p-AKT pathway was not dose dependent among the doses tested and was maximally inhibited at 25mg BID, and this is the FDA approved dose (8). We will initiate treatment of critically ill patients with COVID-19 at an initial dose of 25 mg duvelisib BID, and dose-deescalate to 15 mg BID if patients receive concomitant drug that is a strong CYP3A4 inhibitor.

5.2 Dosing and Administration

Regimen Description					
Agent	Premedication/Precautions	Dose	Route	Schedule	Treatment Course
Duvelisib/ placebo	Take with 8 oz of water food	25 mg capsule	PO	BID	14 days

5.3 Dose Modification

The investigator will decide whether any AE that occurs is related to study drugs and determine whether dose modification or discontinuation of duvelisib/placebo is required. Treatment of critically ill patients with COVID-19 will be started at an initial dose of 25 mg duvelisib/placebo BID, and dose-deescalate to 15 mg BID if patients receive concomitant drug that is a strong CYP3A4 inhibitor.

5.4 Concomitant medication

Acceptable Concomitant Medications

Patients with severe COVID-19 are ill and will require treatment with standard-of-care drugs or procedures to treat existing signs and symptoms of their disease and to prevent the development of additional disease manifestations. All concomitant medication (including prescribed, over the counter, herbal or vitamin supplements) used by the patient prior to 7 days to enrollment are permitted to be continued under the supervision and discretion of the treating physician. The use of FDA-approved drugs in an “off-label” situation to treat or prevent signs or symptoms of COVID-19 are permitted if they are given under the direction of the treating physician as local standard-of-care. Any drug with known anti-viral activity that has been accepted by the FDA/CDC/NIH/WHO in published clinical guidance documents as having activity against SARS-CoV-2, or an anti-viral drug that has been approved by a regulatory agency for use as an anti-viral against SARS-CoV-2 is permitted as standard-of-care or as part of a formal clinical study. Co-enrollment in randomized or non-randomized clinical studies of drugs with potential anti-viral activity against SARS-CoV-2 are permitted. For example, the FDA has authorized the unapproved product remdesivir for treatment of suspected or confirmed COVID-19 in adults and children hospitalized with severe disease. As new drugs are developed and introduced into the treatment paradigm for patients with COVID-19, the toxicity profile of these drugs will be compared with the toxicity profile of duvelisib by the study pharmacist. Treatment with an agent (investigational or standard of care) with a toxicity profile that overlaps significantly with that of duvelisib will be an exclusion criterion for subject enrollment. Co-enrollment on a clinical study testing another immune-modulatory drug (i.e., tocilizumab, baracitinib) is not permitted. Determination of whether the mechanism of action of drugs being tested in COVID-19 patients have an immune-modulatory effect as their primary proposed mechanism of action will be made monthly by the study pharmacist based upon a review of data available in www.clinicaltrials.gov, and an updated list of non-permitted immune-modulatory drugs will be provided to the research staff for the purposes of subject screening. All medications should be reported to the investigators and recorded in the concomitant medications page.

It is anticipated that participants may be treated with antibacterial agents, either for concomitant infection, or bacterial superinfection, anti-coagulants, and passive antibody treatment (immune plasma or purified antibodies reactive to SARS-CoV-2 epitopes). The final decision for antibiotics (need, drug[s] and dose) and other medications will be made by the treating physician (except as noted below under Prohibited Medications). Concomitant use of medications that are sensitive CYP450 substrates (Appendix C) are prohibited, unless

Protocol Title: Duvelisib Ameliorates Manifestations of Pneumonia in Established Novel Coronavirus Infection (DAMPEN-CI)

absolutely necessary. If concomitant use of a medication which is a CYP450 substrates is required, then adverse events (AEs) should be monitored every 2 days.

Pneumocystis jirovecii pneumonia (PJP) and CMV prophylaxis.

Since duvelisib or placebo exposure is only 14 days, the risk of developing PJP or CMV viremia in this study is low, and specific antimicrobial prophylaxis with Bactrim (PJP) and valganciclovir (CMV) for a 14 period would be of limited clinical benefit given the short time of exposure to duvelisib, and prophylaxis with Bactrim and/or valganciclovir could lead to a higher incidence of blood cytopenia which might trigger stopping the study drug. Given the short term exposure to duvelisib, no PJP or CMV prophylaxis is mandated by the protocol, although treating physician may prescribe such medications if deemed to be in the interests of the subject.

Prohibited Medications and Food

Concomitant medications will be tracked daily during duvelisib administration. Patients on strong inhibitors of CYP3A (Appendix B) will receive a reduced dose of duvelisib of 15 mg PO BID (or matched placebo). Initiation of medications known to be strong inducers or inhibitors of CYP3A should be avoided unless deemed to be necessary by the PI. In this instance, patients should be carefully monitored and the duvelisib dose reduced to 15 mg PO BID if the patient was started on a CYP3A inhibitor. Please see Appendix B for known potent inhibitors and inducers of CYP3A. Other anti-neoplastic drugs, radiotherapy and other investigational drugs other than anti-viral and other non-immunomodulatory drugs to treat signs and symptoms of COVID-19, as described above, are prohibited during the study period. Concomitant use of an immunomodulator or immunosuppressant (Appendix E) such as IL-6 inhibitors, TNF inhibitors, anti-IL-1 agents, and JAK inhibitors while on study or within 5 half-lives or 30 days (whichever is longer) prior to randomization is prohibited.

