APPENDIX B: POTENT INHIBITORS AND INDUCERS OF CYP3A4 (FDA reference 2014)

Effect on CYP3A	Drug Class	Medications
Moderate to Strong CYP3A Inhibitors	Antibiotics	chloramphenicol, ciprofloxacin, clarithromycin, erythromycin, telithromycin
	Antiemetic	aprepitant
	Antifungals	ketoconazole, fluconazole, itraconazole, posaconazole, voriconazole
	Antiviral protease inhibitors	amprenavir, atazanavir, boceprevir, cobicistat, darunavir, elvitegravir, fosamprenavir, indinavir, lopinavir, nefinavir, ritonavir, saquinavir, telaprevir, tenofovir, tipranavir
	Calcium-channel blockers	diltiazem, mibefradil, verapamil
	Foods/herbs	grapefruit, grapefruit juice, Seville oranges
	Serotonin antagonist	nefazodone
	Tyrosine kinase inhibitor	imatinib
	Vasopressin antagonist	conivaptan
Moderate to Strong CYP3A Inducers	Antibiotics	nafcillin, rifampin
	Anticonvulsants	carbamazepine, phenobarbital, phenytoin
	Antiviral reverse transcriptase inhibitors	efavirenz, etravirine
	Endothelin receptor antagonist	bosentan
	Foods/herbs	St. John's wort
	Wakefulness-promoting agent	modafinil

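### The 15 mg BID dose applies only to strong CYP3A inhibitors, but Appendix B, the list cited for it, mixes moderate and strong inhibitors without telling them apart

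*Combined protocol and SAP*

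**What the plan says.** The starting dose is 25 mg BID for up to 14 days. Section 5.3 allows staff to "dose-deescalate to 15 mg BID if patients receive concomitant drug that is a strong CYP3A4 inhibitor", and the dose justification in Section 5.1 says the same. Section 5.4, under prohibited medications, restates the rule and attaches a list to it: "Patients on strong inhibitors of CYP3A (Appendix B) will receive a reduced dose of duvelisib of 15 mg PO BID" (or matched placebo).

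Section 5.4 then deals with drugs started during the study: "Initiation of medications known to be strong inducers or inhibitors of CYP3A should be avoided unless deemed to be necessary by the PI". In that event the patient is to be monitored and "the duvelisib dose reduced to 15 mg PO BID if the patient was started on a CYP3A inhibitor". The reader is next sent back to the list: "Please see Appendix B for known potent inhibitors and inducers of CYP3A".

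Appendix B describes its contents as potent in its title, but its only inhibitor category carries the label "Moderate to Strong CYP3A Inhibitors". That category covers nine drug classes.

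**The concern.** The rule and its lookup table do not have the same scope. The rule names strong inhibitors. The table given to identify them includes, by its own label, moderate ones as well, and does not show which are which. A coordinator or pharmacist who finds a patient's drug in Appendix B and acts on that would reduce the dose for some patients whom the rule leaves at 25 mg BID. One who holds to the word *strong* has to classify the drug without help from the table.

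What is at stake is the dose given to some patients in the duvelisib arm. Section 5.1 chose 25 mg BID because pathway inhibition was already maximal there, so an unintended move to 15 mg BID should be ruled out.

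The investigator check on starting strong agents gives some protection, but it is worded for initiation and for strong agents. Medicines "used by the patient prior to 7 days to enrollment are permitted to be continued under the supervision and discretion of the treating physician" fall outside it, and so do moderate inhibitors whenever they are started.

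**Working it through.** **Step 1: compare the trigger wording.**

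| Place | Trigger for 15 mg BID | Cites Appendix B? |
|---|---|---|
| 5.1, dose justification | strong CYP3A4 inhibitor | no |
| 5.3 | strong CYP3A4 inhibitor | no |
| 5.4, patients already on an inhibitor | strong CYP3A inhibitor | yes, as the list |
| 5.4, inhibitor newly started | CYP3A inhibitor; the lead-in ties it to the strong agents of the sentence before | yes, in the next sentence |
| Appendix B | no dose rule; category reads moderate to strong | n/a |

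**Step 2: count the Appendix B inhibitor entries.** Antibiotics 5, antiemetic 1, antifungals 5, antiviral protease inhibitors 15, calcium-channel blockers 3, foods and herbs 3, serotonin antagonist 1, tyrosine kinase inhibitor 1, vasopressin antagonist 1.

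5 + 1 + 5 + 15 + 3 + 3 + 1 + 1 + 1 = 35. Entries marked as strong or as moderate: 0.

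**Step 3: look for a separating list elsewhere.** Appendices C and D list substrates, not inhibitors. No section defines *strong*, gives a strong-only list, or states a dose for moderate inhibitors.

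**Step 4: dose under each reading, for a patient on a listed moderate inhibitor.** Inputs: 25 mg and 15 mg strengths and 28 capsules per patient (Section 4.2.2); twice daily for 14 days (Section 5.2).

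- Rule as written: 2 × 25 = 50 mg per day; 28 × 25 = 700 mg per course.
- List used as the trigger: 2 × 15 = 30 mg per day; 28 × 15 = 420 mg per course.
- Difference: 50 − 30 = 20 mg per day; 700 − 420 = 280 mg, and 280 / 700 = 40%.

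The 280 mg is a ceiling. It needs the reduced dose on all 14 days. A later start of the co-medication makes it smaller, and so does early discharge, since Section 4.2.5 stops study drug at discharge. The plan states no figure of its own on this point to reproduce.

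**The case against.** The best reply is that the text already settles the matter. All three dose rules say *strong*, 5.1 and 5.3 do not mention the appendix, and a category label in an appendix is not a dosing instruction. On that view a patient on a moderate inhibitor stays at 25 mg BID, and the reference in 5.4 means the strong drugs among those listed. This stands: a reader might infer that the protocol contains two competing dose rules with no way to choose between them, and the documents do not support that. There is one rule. What remains is that the table supplied for applying it cannot identify the drugs it covers.

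Three other stronger readings should also be set aside.

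- *Sites will dose differently.* The trial starts at Emory and only hopes to open other sites (Section 20), and study drug is over-encapsulated and stored at the Emory pharmacy (Sections 4.2.2 and 4.2.3). Variation is possible, since no section assigns the classification of inhibitors to anyone, but the documents do not show that it would occur.
- *Patients lose 40% of their exposure, or some efficacy.* The figures are nominal milligrams in patients whose co-medication itself inhibits CYP3A. The documents give no exposure or response data at 15 mg BID with a moderate inhibitor.
- *The 5.4 clause on newly started drugs extends the reduction to any CYP3A inhibitor.* Its lead-in refers back to strong agents, so the missing word is a drafting slip.

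Formatting that marked strength could have been lost when the PDF was read. No legend or footnote suggests that it was, but the count of unmarked entries applies to the extracted text.

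**Conclusion.** The point holds as a mismatch between a rule and the list cited for it. Using Appendix B as the trigger would give 15 mg BID to a patient on a moderate inhibitor, whom Sections 5.1, 5.3 and 5.4 keep at 25 mg BID. The nominal difference is 20 mg per day, with a ceiling of 280 of 700 mg.

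This rests on two things: that the appendix label is accurate in saying the list includes moderate inhibitors, and that no strength marking was lost in extraction. Which entries are moderate, how many patients take one, and whether the lower dose would matter clinically are not known from the documents. Sample size, power, type I error and the planned analyses are unaffected. It is a minor clarification, worth making because it can change the dose given and costs almost nothing.

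**What to change.** Split the Appendix B inhibitor row into Strong and Moderate, using the FDA reference named in the appendix title, and state there that only the Strong entries trigger 15 mg BID. In the Section 5.4 clause on newly started drugs, insert *strong* before the reference to a CYP3A inhibitor. The cost is one relabelled table, one added statement and one added word.

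If the sponsor instead means every listed inhibitor to trigger the reduction, keep the single row and change *strong* to *moderate or strong (Appendix B)* in the dose-reduction sentences of 5.1, 5.3 and 5.4 only. The 5.4 sentence that restricts starting strong inducers or inhibitors should stay as it is; editing it too would widen a clinical restriction, which is a separate decision. The cost is a wording change in three sections.

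Neither route alters the design, sample size or analysis.
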